2 ELIGIBILITY ASSESSMENT AND ENROLLMENT

2.1 ELIGIBILITY CRITERIA

2.1.1 Inclusion Criteria

2.1.1.1 Stage 1 Eligibility (Cohort 1 and 2)

➤ Cohort 1

- Histologically confirmed by NCI Laboratory of Pathology intra-cranial or spinal **RELA-fusion** ependymoma of grade I, II or III.
- Has received two or fewer prior chemotherapy regimens

➤ Cohort 2

- Histologically confirmed by NCI Laboratory of Pathology intra-cranial or spinal **RELA-fusion** ependymoma of grade I, II or III.
- Has received more than two prior chemotherapy regimens

2.1.1.2 Stage 2 Eligibility (Cohorts 3 and 4)

➤ Cohort 3

- Histologically confirmed by NCI Laboratory of Pathology intra-cranial or spinal **non RELA-fusion** ependymoma of grade I, II or III.
- Has received two or fewer prior chemotherapy regimens

➤ Cohort 4

- Histologically confirmed by NCI Laboratory of Pathology intra-cranial or spinal **non RELA-fusion** ependymoma of grade I, II or III.
- Has received more than two prior chemotherapy regimens

2.1.1.3 Patients must have an evidence of tumor progression as defined in Section **2.2.2.1**.

2.1.1.4 Patients must have had prior radiation therapy.

2.1.1.5 Patients must be ≥ 18 years old. Currently, no dosing or adverse event data is available on the use of marizomib in patients < 18 years of age; therefore only adults are included in this study. Patients < 18 years of age will be eligible for future pediatric trials.

2.1.1.6 Patients must have a Karnofsky performance status of ≥ 60 (see **Appendix A**).

2.1.1.7 Patients must have adequate organ and marrow function as defined below:

- leukocytes $\geq 3,000/\mu\text{L}$
- absolute neutrophil count $\geq 1,500/\mu\text{L}$
- platelets $\geq 100,000/\mu\text{L}$
- hemoglobin ≥ 10 gm/dL (can be achieved by transfusion)
- AST(SGOT)/ALT(SGPT) ≤ 2.5 X institutional upper limit of normal
- Bilirubin < 1.5 mg/dL

- Creatinine up to 1.5-times upper institutional limits OR eGFR within normal as predicted by the CKD-EPI equation (≥ 60 mL/min/1.73m²).
- Negative urine protein or urine protein concentration ≤ 60 mg/dL

2.1.1.8 The effects of marizomib on the developing human fetus are unknown. For this reason, women of child-bearing potential and men must agree to use adequate contraception (hormonal or barrier method of birth control; abstinence) prior to study entry and for the duration of study participation and up to 30 days after the last dose of the drug. Should a woman become pregnant or suspect she is pregnant while she or her partner is participating in this study, she should inform her treating physician immediately.

2.1.1.9 Ability of subject to understand and the willingness to sign a written informed consent document.

2.1.2 Exclusion Criteria

2.1.2.1 Anticancer treatment within designated period of time before enrollment including:

- surgery within 14 days
- needle or core biopsy within 7 days
- prior cytotoxic therapy within 28 days,
- vincristine within 14 days
- nitrosoureas within 42 days,
- procarbazine administration within 21 days
- non-cytotoxic agents, e.g., interferon, tamoxifen, thalidomide, cis-retinoic acid (radiosensitizer does not count) within 7 days; Avastin within 21 days. Any questions related to the definition of non-cytotoxic agents should be directed to the NCI Principal Investigator.

2.1.2.2 Treatment with any investigational agent within 28 days before enrollment.

2.1.2.3 History of any other cancer (except non-melanoma skin cancer or carcinoma in-situ of the cervix), unless patient is in complete remission and off all therapy for that disease for a minimum of 3 years.

2.1.2.4 History of allergic reactions attributed to compounds of similar chemical or biologic composition to marizomib.

2.1.2.5 Uncontrolled intercurrent illness including, but not limited to, ongoing or active infection, symptomatic congestive heart failure, unstable angina pectoris, cardiac arrhythmia, or psychiatric illness/social situations that would limit compliance with study requirements.

2.1.2.6 Inadequately controlled hypertension (defined as systolic blood pressure > 140 mmHg and/or diastolic blood pressure > 90 mmHg).

2.1.2.7 Current active hepatic or biliary disease (with exception of patients with Gilbert's syndrome, asymptomatic gallstones, or stable chronic liver disease per

investigator assessment).

- 2.1.2.8 New York Heart Association (NYHA) Grade II heart failure or greater or history of hospitalization for congestive heart failure diagnosis within 12 months prior to enrollment.
- 2.1.2.9 History of myocardial infarction or unstable angina within 3 months prior to enrollment.
- 2.1.2.10 A marked baseline prolongation of QT/QTc interval (e.g., repeated demonstration of a QTc interval >480 milliseconds (ms) (CTCAE grade 1) using Frederica's QT correction formula.
- 2.1.2.11 A history of additional risk factors for TdP (e.g., heart failure, hypokalemia, family history of Long QT Syndrome).
- 2.1.2.12 Current use of concomitant medications that prolong the QT/QTc interval
- 2.1.2.13 History of stroke or transient ischemic attack within 3 months prior to enrollment.
- 2.1.2.14 Pregnant women are excluded from this study because marizomib's potential for teratogenic or abortifacient effects is unknown. Because there is an unknown but potential risk for adverse events in nursing infants secondary to treatment of the mother with marizomib, breastfeeding should be discontinued if the mother is treated with marizomib.
- 2.1.2.15 Patients receiving combination antiretroviral therapy for treatment of Human Immunodeficiency Virus (HIV) or active anti-viral treatment for Hepatitis A, B or C infection. Anti-viral therapy, when combined with marizomib, poses a potential for pharmacokinetic interactions. Marizomib also increases immunosuppression, placing patients at an increased risk of acquiring lethal infections. Appropriate studies will be undertaken in patients receiving combination antiretroviral therapy when indicated.

2.1.3 Inclusion Criteria for Pregnancy Cohort (P)

Because the drug manufacturer would like to study the effect of the study therapy on pregnancy, and because the required information cannot be collected unless a subject is enrolled per ruling of the OGC, the following additional groups of subjects may be enrolled if necessary. The subjects enrolled in this cohort will not meet the inclusion and exclusion criteria found in [2.1.1](#) and [2.1.2](#).

- A child whose parent (male or female) is/was an active participant in the study at any time during the child's gestation. Active participant is defined as having received at least one dose of study therapy through 6 months after the last dose of study therapy.

OR

- An expectant mother of child whose father is/was an active participant in the study at any time during the child's gestation. The father must have received at least one dose of study therapy. Active participant is defined as having received at least one dose of study therapy through 6 months after the last dose of study therapy.
- The expectant mother must be age 18 or older and must have the capacity to provide informed consent.

2.1.4 Recruitment Strategies

Participants will be recruited from the patient base who seek consultation for recurrent ependymoma or they may be pre-existing patients at NIH with ependymoma who have tumor progression. Ependymoma is a very rare disease entity with few treatment options and all attempts will be made to include under-represented minorities with ependymoma. This protocol may be abstracted into plain language announcements posted on NIH websites and on NIH social media platforms.

2.2 SCREENING EVALUATION

2.2.1 Screening activities performed prior to obtaining informed consent

Minimal risk activities that may be performed before the subject has signed a consent include the following:

- Email, written, in person or telephone communications with prospective subjects
- Review of existing medical records to include H&P, laboratory studies, etc.
- Review of existing MRI, x-ray, or CT images
- Review of existing photographs or videos
- Review of existing pathology specimens/reports from a specimen obtained for diagnostic purposes

A waiver of consent for these activities has been requested in section [12.8.3](#).

2.2.2 Screening activities performed after a consent for screening has been signed

The following activities will be performed only after the subject has signed the consent for this study for screening. Assessments performed at outside facilities or on another NIH protocol (01-C-0129 CCR Screening protocol or 16-C-0151 NOB Natural History Protocol) within the timelines below may also be used to determine eligibility once a patient has signed the consent. The screening evaluation must be completed within 14 timelines noted in Section [2.4](#) unless otherwise noted:

2.2.2.1 Imaging

- MRI head and/or spine with gadolinium to confirm progressive disease. MRI parameters should follow the specifications detailed in [Appendix B](#). If the steroid dose is increased between the date of imaging and consent, a new screening MRI is required after patient has been on a stable steroid dose for at least 5 days.
- Patients with prior therapy that included interstitial brachytherapy or stereotactic radiosurgery must have confirmation of true progressive disease rather than radiation necrosis based upon either PET or Thallium scanning, MR spectroscopy, or surgical/pathological documentation of recurrent disease (Screening only).

2.2.3 History and physical examination

- Complete medical history and physical examination, including height, weight, vital signs, EKG, and Karnofsky performance status ([Appendix A](#))
- Neurologic Exam (See [Appendix A](#))

2.2.4 Laboratory Evaluation

- Hematological profile: CBC with differential and platelet count;
- Biochemical profile: electrolytes, BUN, creatinine, AST, ALT, total bilirubin, calcium,

phosphorus, albumin, magnesium, uric acid;

- Serum or urine pregnancy test for female participants of childbearing age (in the absence of prior hysterectomy) (7 days prior to treatment registration);
- Urinalysis

2.2.5 Histologic confirmation

- Histologic confirmation of diagnosis and *RELA* fusion status by NCI Laboratory of Pathology (at any time point prior to treatment). If there is no available tissue samples, biopsy will be performed to confirm the diagnosis and *RELA* fusion status.

For baseline evaluations, please see section 2.4

2.3 PARTICIPANT REGISTRATION AND STATUS UPDATE PROCEDURES

Registration and status updates (e.g., when a participant is taken off protocol therapy and when a participant is taken off-study) will take place per CCR SOP ADCR-2, CCR Participant Registration & Status Updates found [here](#).

2.3.1 Treatment Assignment Procedures (For registration purposes only):

Cohorts

Number	Name	Description
1	Cohort 1	Subjects with intra-cranial or spinal RELA -fusion ependymoma who have had none, 1 or 2 prior chemotherapies.
2	Cohort 2	Subjects with intra-cranial or spinal RELA -fusion ependymoma who have had more than 2 prior chemotherapies.
3	Cohort 3	Subjects with intra-cranial or spinal non RELA -fusion ependymoma who have had none, 1 or 2 prior chemotherapies.
4	Cohort 4	Subjects with intra-cranial or spinal non RELA -fusion ependymoma who have had more than 2 prior chemotherapies.
P	Cohort P	Children who may have been exposed to the study drug in utero OR expectant mothers of children who may have been exposed to the study drug in utero if mother not in a treatment cohort

Arm

Number	Name	Description
1	Arm 1	Marizomib at days 1, 8 and 15 of each 28-day cycle
P	Pregnancy evaluation	Data collection on pregnancy, birth and health of child up to 1 year.

Arm assignment

Subjects in Cohort 1, 2, 3 and 4 will be directly assigned to Arm 1.

Subjects in Cohort P will be directly assigned to Arm P.

2.4 BASELINE EVALUATION

Tests done at screening do not need to be repeated at baseline if performed in designated time frame prior to start of study drug.

Within 14 days prior to first dose:

- MRI of the head and/or spine with gadolinium as specified in [Appendix B](#).
- Archived tumor samples will be collected to do molecular studies as described in Section [5.3](#). If the patient has previously been on another study at NIH, and the required molecular profiling has been done, then additional pathology material may not be needed (any time prior to treatment initiation).
- The MDASI-BT and/or MDASI-SP . The choice of instrument will be based on the location of the index lesion for study enrollment. This may be in the brain (MDASI-BT), spine (MDASI-SP) or both (completing both instruments if lesions in the brain and spine are being followed for response). (For English speaking subjects only).
- Research blood for SNP Studies (See section [5.1.2](#))
- Research blood for Pharmacogenomic Studies (Cohort 1 only) (See section [5.1.2](#))
- Concomitant Medications
- Adverse events
- EKG (within 3 days prior to first dose)
- Subjects will complete and sign an NIH advanced directives form which is mandatory on this study.

3 STUDY IMPLEMENTATION

3.1 STUDY DESIGN

3.1.1 Cohorts 1-4:

[figure not shown]
This is a phase II study to evaluate the efficacy of treatment with marizomib in *RELA*-fusion recurrent ependymoma and non *RELA*-fusion recurrent ependymoma. In the stage 1 of study, there will be simultaneous accrual into Cohorts 1 and 2. For Cohort 1, 9 patients with *RELA*-fusion ependymoma and none, 1, or 2 or prior chemotherapies will be enrolled. For Cohort 2, 9 patients with *RELA*-fusion ependymomas and >2 prior chemotherapies. If we find evidence of clinical activity of marizomib, (4 or more patients in Cohort 1 are progression free at 6 months), we will proceed to stage 2, otherwise we will terminate the trial.

At stage 2, we will enroll patients into 2 cohorts: 16 patients with non *RELA*-fusion ependymoma who had none, 1 or 2 prior chemotherapies (Cohort 3) and 16 patients with non *RELA*-fusion ependymoma who had more than 2 prior chemotherapies (Cohort 4).

During stage 2, enrollment into Cohorts 3 and 4 will occur simultaneously. Please see [Schema 1](#).

One cycle is 4 weeks (+/- 3 days). Patients will be treated with IV marizomib at 0.8 mg/m² on days 1, 8 and 15 of each 28-day cycle until off treatment criteria are met (Section 3.8.1).

Schema 1: STUDY DESIGN

3.1.2 Cohort P – Pregnancy Related Study Procedures, Birth and Health of Child

After signing the pregnant partner consent document, subjects in Cohort P, as well as women who may have become pregnant on any of the treatment cohorts will be asked to sign form [NIH-1208](#), a request for release of medical information. Releases will be required for both the exposed child and for the expectant mother.

3.2 DRUG ADMINISTRATION

Marizomib will be administered at 0.8 mg/m² IV over at least 10 minutes (+10 minutes) (see section 14.1.5).

Patients should be premedicated with ondansetron 8 mg IV or prochlorperazine 10 mg IV 60 minutes (+/- 30 minutes) prior to marizomib infusion to prevent nausea or vomiting.

The dose will be determined using the body surface area (BSA) calculated prior to each day 1 unless significant (> 3 kg) weight loss or gain is observed during a cycle. The BSA will be calculated from the height obtained at screening and the weight obtained at day 1 visit. The dose will be rounded to the nearest 0.1 mg.

On Cycle 1, Day 1, 8 and 15 vital signs will be taken within 10 minutes before the marizomib infusion and 10 (+/- 5) minutes, 30 (+/- 10) minutes, and 1 hour (+/- 15 minutes) following the marizomib infusion. For all subsequent cycles, vital signs will be assessed prior to the marizomib infusions and approximately 30 (+/- 10) minutes following each infusion.

Investigators should start assessing patients for CNS AEs (Section 8.1.6) after the first marizomib dose, although frequently these AEs do not appear until Cycle 2 or later. Dose modifications guidelines for CNS adverse events are outlined in Table 2. A scale for rating severity of hallucinations is provided in Appendix C.

Patients should be warned against driving or operating machinery if they develop CNS adverse events while receiving marizomib.

3.3 DOSE MODIFICATIONS

Dose modifications are explained in the Table 2, Table 3 and Table 4

If the dose was reduced for AEs, there will be no dose re-escalation in subsequent treatment cycles. After Dose level -3, no more dose reduction is allowed and patient will be taken off treatment.

Table 1: Marizomib Dose Reduction Levels

Dose Level	Weekly dose	Treatment Schedule
Starting dose	0.8 mg/m ²	Days 1, 8, and 15 (28-day cycle)
Dose level -1	0.7 mg/m ²	Days 1, 8, and 15 (28-day cycle)
Dose level - 2	0.55 mg/m ²	Days 1, 8, and 15 (28-day cycle)
Dose level - 3	0.4 mg/m ²	Days 1, 8, and 15 (28-day cycle)

Table 2: Marizomib Dose Modification Instructions

Marizomib-Related Adverse Event	Severity	Recommended Dose Modification
Central Nervous System		
Common CNS AEs including: ataxia, dizziness, gait disturbance, balance disorder, fall, dysarthria, confusion. For hallucinations management, please, see section 3.3.1	Grade 1	Maintain current MRZ dose schedule without dose modification.
	Grade 2	Consider other supportive treatment (see Table 4); generally no dose-reductions are recommended. Consider dose-reduction if intolerable by patient due to interference with daily routine and/or if duration of event lasts longer than 3 days.
	Grade 3	At the next scheduled MRZ dose administration, dose-reduce one dose level. If AE has not resolved to \leq Grade 1 (or baseline), skip the MRZ dose and resume with the next scheduled dose at reduced level (Table 1). In addition, consider other supportive treatment (see Table 4)
	Grade 4	Stop MRZ until resolution to \leq Grade 1 (or baseline). If re-challenge is an option, reduce MRZ dose level (Table 1). Treatment should be permanently discontinued if the toxicity does not resolve to grade 1 or less within 2 weeks.
Gastrointestinal		
Nausea, Vomiting	Grade 1 or 2	Implement prophylactic anti-emetic regimen according to local guidelines. Maintain current MRZ dose schedule without dose modification. If (re)occurrence despite appropriate prophylaxis, dose-reduce one dose level (Table 1) at the next scheduled MRZ dose administration.
	Grade 3 or 4	Implement prophylactic anti-emetic regimen according to local guidelines. If (re)occurrence despite appropriate prophylaxis, dose-reduce one dose level (Table 1) at the next scheduled MRZ dose administration. In addition, consider other supportive treatment (Table 4).

Marizomib-Related Adverse Event	Severity	Recommended Dose Modification
Other Adverse Events		
	Grade 2	Maintain current MRZ dose schedule without dose modification. Consider dose-reduction (Table 1) if intolerable by patient due to interference with daily routine and/or not resolved to \leq Grade 1 (or baseline) at the next scheduled MRZ dose administration.
	Grade 3	At the next scheduled MRZ dose administration, dose-reduce one dose level (Table 1). If AE has not resolved to \leq Grade 1 (or baseline), skip the MRZ dose and resume with the next scheduled dose at reduced level.
	Grade 4	Stop MRZ until resolution to \leq Grade 1 (or baseline). If re-challenge is an option, reduce MRZ dose level (Table 1). If toxicity continues beyond 2 weeks, consider permanent discontinuation.

3.3.1 Hallucinations management

Patients and care givers are warned about the possibility of hallucinations. Hallucinations are graded/characterized by the Lukoff criteria (Hallucination Severity Scale, **Appendix C**) and management guidelines based on these criteria are provided below in **Table 3**. Both therapeutic and prophylactic use of anti-psychotics may be considered for management of hallucinations. While there has been no correlation between medical history of mental illness and the incidence of hallucinations, patients with preexisting mental illness should be monitored closely and consideration given to prophylactic anti-psychotic dose increase.

Table 3: Hallucinations management:

	Recommended actions
Very Mild OR Mild OR Moderate	No marizomib dose reduction needed
Moderately severe, Related to marizomib	Stop marizomib until resolution to “Very Mild or Mild or Moderate” (or baseline). May use quetiapine fumarate or olanzapine as indicated. If hallucination resolves with treatment, consider continuing treatment and dosing on same schedule as before. If hallucination returns while on anti-psychotic, then dose reduction at the next dose (Table 1) is warranted.

	Recommended actions
Severe, Related to marizomib	At the next scheduled marizomib dose administration, dose-reduce one dose level (Table 1). If AE has not resolved to “Very Mild or Mild or Moderate” (or baseline), skip the marizomib dose and resume with the next scheduled dose at reduced level. In addition, consider other supportive treatment as per section (Table 4)
Extremely severe, Related to marizomib	Stop MRZ until resolution to “Very Mild or Mild or Moderate” (or baseline). If re-challenge is an option, reduce MRZ dose level (Table 1). Treatment should be permanently discontinued if the toxicity does not resolve to grade 1 or less within 2 weeks.

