1.2.5.1 Neurotoxicity's management

Based on findings from preclinical and clinical studies, marizomib, particularly when administered as a 10 minute infusion, crosses the BBB, resulting in multiple CNS AEs ranging in severity from Grade 1 to Grade 4. CNS AEs appear to be dose related as more are observed at the 1.0 mg/m² dose and in general, respond to dose reduction. Due to concern for CNS AEs, in this study we will use marizomib at 0.8 mg/m² and there will be no dose escalation. CNS AEs are generally treated with dose modifications and appropriate supportive treatments as indicated. If resolution does not occur following these measures, consider underlying disease progression or other causes. The most common CNS AEs include the following:

Hallucinations: Hallucinations are frequently observed in ongoing marizomib studies in glioblastoma ranging in incidence from 19-37%. In general, hallucinations tend to be grade 1 or 2 but one grade 4 event, requiring hospitalization, has been observed. The hallucinations are transient and self-limiting. Visual hallucinations are more common than auditory and there is a trend for increased incidence with age. Hallucinations are frequently more disturbing to the caregiver than to the patient. Hallucinations are usually managed successfully by dose reduction and are an infrequent reason for treatment discontinuation.

Ataxia: Events of gait disturbance, balance disorders/dizziness, and ataxia are frequently observed in the ongoing studies in glioblastoma, MRZ 108 and MRZ 112, with a range of 5-28%. These adverse effects which are cerebellar in nature are suspected to be related to the predominance of proteasomes in the cerebellar region. The events typically occur within the 1st or 2nd cycle, are usually grade 1-2 but events of ataxia have required hospitalization. Patients are treated with dose modifications and steroids as needed without leading to permanent discontinuation of marizomib. As a result of these events, patients are warned not to operate heavy machinery and/or drive if experiencing cerebellar side-effects.

Headache: Headaches have been reported with administration of marizomib across indications and dosages. While headaches are commonly present due to the underlying disease in GBM, in the ongoing studies with marizomib in GBM, incidence of treatment emergent headaches ranges from 25-53%. Dose modifications and treatment with steroids are recommended for management of headaches in glioblastoma.

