16.3 APPENDIX C: HALLUCINATION SEVERITY SCALE

In addition to the adverse event (AE) data recorded for all AEs, an additional rating of the severity of hallucinations will be recorded in the CRF using the following criteria [32].

Since hallucinations are an AE of interest, the type of hallucination, start and stop date, and severity are to be recorded in the CRF.

Severity	Definition
Very mild	While resting or going to sleep, sees visions, smells odors or hears voices, sounds, or whispers in the absence of external stimulation, but no impairment in functioning.
Mild	While in a clear state of consciousness, hears a voice calling the individual's name, experiences non-verbal auditory hallucinations (e.g., sounds or whispers), formless visual hallucinations or has sensory experiences in the presence of a modality relevant stimulus (e.g., visual illusions) infrequently (e.g., 1-2 times per week) and with no functional impairment.
Moderate	Occasional verbal, visual, gustatory, olfactory or tactile hallucinations with no functional impairment OR non-verbal auditory hallucinations/visual illusions more than infrequently or with impairment.
Moderately Severe	Experiences daily hallucinations OR some areas of functioning are disrupted by hallucinations.
Severe	Experiences verbal or visual hallucinations several times a day OR many areas of functioning are disrupted by these hallucinations.
Extremely Severe	Persistent verbal or visual hallucinations throughout the day OR most areas of functioning are disrupted by these hallucinations.

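### Table 3, hallucinations: the 'Extremely severe' row sets restart and permanent discontinuation on two unlinked scales, and the hold rule is looser for 'Severe' than for 'Moderately severe' if read literally

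*Combined protocol and SAP*

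**What the plan says.** Section 3.3.1 names the scale on which Table 3 is built: "Hallucinations are graded/characterized by the Lukoff criteria (Hallucination Severity Scale", with a pointer to Appendix C (section 16.3). Appendix C has six worded levels, from Very mild to Extremely severe, and no numeric grades.

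Three rows of Table 3 matter here:

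- **Moderately severe:** "Stop marizomib until resolution to “Very Mild or Mild or Moderate” (or baseline). May use quetiapine fumarate or olanzapine as indicated". If the event resolves with treatment, dosing on the same schedule may be considered. A dose reduction follows only if hallucinations return on an anti-psychotic.
- **Severe:** the dose goes down one level at the next scheduled administration. If the event has not resolved to Moderate or milder (or baseline), the instruction is to "skip the marizomib dose and resume with the next scheduled dose at reduced level".
- **Extremely severe:** "Stop MRZ until resolution to “Very Mild or Mild or Moderate” (or baseline). If re-challenge is an option, reduce MRZ dose level". The row then closes with "Treatment should be permanently discontinued if the toxicity does not resolve to grade 1 or less within 2 weeks".

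Elsewhere, numeric grades are CTCAE version 5.0 (sections 6.4 and 8.1.4). Section 16.3 describes the Appendix C rating as recorded in addition to the usual adverse event data.

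**The concern.** A hold, restart and stopping table has to give one answer for a given patient on a given day. Table 3 appears to fail this in two places. In the 'Extremely severe' row, restart and permanent discontinuation are decided on different scales, with nothing to convert one to the other. Between the 'Moderately severe' and 'Severe' rows, the milder level appears to carry the stricter recovery requirement.

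The stakes are mainly safety. Hallucinations are among the CNS events of clinical interest (section 8.1.6) and have their own reporting provision (section 8.4.3). Section 3.8.1 removes patients from therapy for unacceptable toxicity as defined in section 3.3, so this table helps decide who leaves treatment. Doses reduced for adverse events are not re-escalated (section 3.3), so a reading made once carries forward.

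**Working it through.** No figure in the plan is at issue, so the check sets the texts side by side and follows patients through them.

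**Step 1. The two conditions in the 'Extremely severe' row**

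| | Hold and re-challenge | Permanent discontinuation |
|---|---|---|
| Scale | Appendix C words | Numeric grade |
| Threshold | Moderate or milder | Grade 1 or less |
| Baseline exception | Yes | No |
| Time limit | None | 2 weeks |

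The documents contain no conversion between the two scales.

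**Step 2. A patient at Moderate at 2 weeks.** The hold condition is met, so re-challenge is possible. Whether discontinuation applies depends on whether Moderate counts as grade 1 or less, which is not stated. Moderate is the third of six levels and is itself mixed. One branch of its definition has no functional impairment. The other covers non-verbal auditory hallucinations or "visual illusions more than infrequently or with impairment". The protocol does not settle this patient's status.

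**Step 3. A patient back at a baseline above grade 1.** The hold condition is met through its baseline exception. The discontinuation sentence has no such exception, so its condition is failed. This conflict is in the wording and holds under any mapping between the scales.

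**Step 4. Comparison with Table 2.** The CNS Grade 4 row of Table 2 carries the same discontinuation sentence. There the hold condition is also Grade 1 or less (or baseline), so both conditions use one scale. The sentence may have been carried into Table 3 without conversion, but that is an inference.

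**Step 5. 'Moderately severe' against 'Severe' on the day 1, 8, 15 schedule.** Appendix C ranks Severe as worse: several times a day or many areas of functioning disrupted, against daily or some areas. Suppose onset follows the day 1 dose and there is no recovery by day 15.

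| | Day 8 | Day 15 |
|---|---|---|
| Moderately severe throughout | Held | Held, and onward until recovery |
| Severe throughout, literal reading | Skipped | Given at the reduced level |

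**Step 6. A patient who improves from Severe to Moderately severe by day 15.** The Severe row, read literally, says to resume at the reduced level. The Moderately severe row says to stop until recovery. One patient fits two rows, with opposite instructions.

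**The case against.** The strongest reply is that the rows are less disordered than they look.

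- **Dose does rise with severity.** The Severe row mandates a one-level reduction, while the Moderately severe row may return the patient to the same schedule. This stands, and it limits the ordering problem to the hold requirement.
- **The Severe row does check recovery.** It does so once, and the check could be meant to repeat at each scheduled dose. The wording resembles Grade 3 in Table 2. This stands as a possible reading, but the text does not state it. The literal reading still allows resumption without recovery.
- **The clash at Moderate is not proven.** A reader might infer that a patient at Moderate is both eligible for re-challenge and due for discontinuation. That needs Moderate to exceed grade 1, which the documents never say. Re-challenge is also only an option, so the 2-week sentence could be read as a limit on it. What is certain at Moderate is an unanswerable question, not a demonstrated contradiction.
- **The missing baseline exception also occurs in Table 2, Grade 4.** This is so. It makes the gap wider than Table 3 but does not remove it.
- **Table 3 lists recommended actions.** True, but the discontinuation sentence is firmly worded.

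A reader might also go further than the documents allow in three ways. The first is to conclude that identical patients are handled in opposite ways throughout. The row comparison in Step 5 involves patients at different levels; only the improving patient of Step 6 and the patients of the Extremely severe row face competing or unclear instructions.

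The second is a count. Section 1.2.5.1 gives hallucinations "ranging in incidence from 19-37" per cent, and 0.19 × 50 = 9.5 to 0.37 × 50 = 18.5 patients. That is incidence at any severity in glioblastoma studies, and the same section says events tend to be grade 1 or 2, with one grade 4 event. Most would fall outside the disputed rows. The 50 also assumes that stage 2 opens; the 18 stage 1 patients alone give 0.19 × 18 = 3.4 to 0.37 × 18 = 6.7.

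The third is an effect on PFS6. PFS runs to confirmed progression (section 6.3.6). Removal from therapy is not an event, and patients without progression stay on MRI follow-up (section 3.5.2).

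**Conclusion.** The point holds in two parts. First, the Extremely severe row cannot be applied consistently. Its two conditions use unlinked scales, so a patient at Moderate at 2 weeks cannot be classified, and a patient at a baseline above grade 1 meets one condition and fails the other. This rests on the current wording and on the absence of any mapping; it does not assume that Moderate exceeds grade 1.

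Second, the hold requirement is not ordered by severity between Moderately severe and Severe. This rests on reading the Severe row's single recovery check literally. If a repeated check was intended, the defect is that the text does not say so.

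The consequence is for patient safety and for consistent use of the removal criterion in section 3.8.1. The number of patients affected cannot be derived from the documents. Nothing shown here changes PFS6, the operating characteristics in Table 7 or the sample size. The change should be made, but it is a correction to a management table and not a threat to the design.

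**What to change.** The sponsor's clinical team should reconcile the rows of Table 3 with each other and with Appendix C:

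1. State the recovery and discontinuation conditions of the Extremely severe row on one scale, or give an explicit mapping between Appendix C levels and numeric grades.
2. Treat baseline the same way in both conditions of that row.
3. Reconcile the recovery conditions of the Moderately severe and Severe rows. Say whether the recovery check in the Severe row repeats, and which row governs a patient who improves from Severe to Moderately severe.

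The choice of rule is a clinical decision for the sponsor, and none is proposed here. The cost is amended wording in one table, with no added visits, procedures or data.
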